#### Pharmacovigilance.

The study will be paused to assess the safety of study continuation using the following SRs that will be applied to all study subjects throughout the trial:

- 1. An SAE that is determined to be possibly, probably, or definitely related to the study product;
- 2. An AE related to the study product that the PI, RM, and/or the sponsor's PVG MD agree jeopardizes the subject's health or safety;
- 3. An AE related to the study product that requires medical or surgical intervention to prevent occurrence of an SAE;
  - 4. A post-infusion, coagulation function assay result that is abnormal and also greater than a 20% change from the baseline value recorded for prothrombin time and international normalized ratio (PT/INR) and/or activated partial thromboplastin time (aPTT) (eg, a subject who has a baseline INR of 1.0 with a post-infusion INR of 1.3 will activate an SR, because this is an abnormal coagulation function assay result that is also a greater than 20% change from the pre-infusion assay result); and/or
- 5. Post-infusion development of deep vein thrombosis (DVT), cardiac ischemia, pulmonary embolism (PE), or hemolysis.

Data and Safety Monitoring Board (DSMB). A designated DSMB will formally review subjects' data following the completion of infusions in each cohort for the purpose of assessing safety. DSMB meetings will be scheduled to maximize the amount of subject data reported to the DSMB through the 28-day follow-up visit. The DSMB will have at a minimum all data through the 7-Day Follow Up Visit. Following each meeting, the DSMB will provide the sponsor with a recommendation about proceeding with infusions in the subsequent cohort. Following the meeting to review Cohort 3 data, the DSMB will provide a recommendation about proceeding with the next planned FDP trial. After the receipt and consideration of each DSMB recommendation, the sponsor will make a final determination about proceeding to the next cohort or the next FDP trial.

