## 11.1.2.2. Exploratory Analyses Comparing FDP to FFP (Secondary Objective 2)

The analyses conducted for secondary objective 1 will be used to meet secondary objective 2. In addition, descriptive statistics on a post-infusion, abnormal coagulation function assay that is greater than a 20% change in either direction from baseline for PT/INR and/or aPTT values will be presented using separate shift tables. Shift tables based on the upper limit of normal (ULN) will also be provided for D-dimer, PF 1+2, TAT, and C3a des Arg.

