Just prior to first infusion, subjects will be randomized to a treatment sequence, or schedule, that determines which product, FDP or FFP, is to be administered at the first visit. The blinded subjects will receive the alternate product during the second infusion. Product treatment crossover at this higher fixed dose allows for comparison of safety between the two products within the same subject and it allows for the comparison of recovery of select coagulation factors and proteins post-infusion with each product. A two-week interval between each Cohort 3 subject's infusion visits is required regardless of the product treatment sequence.

If any of the stopping rules (SRs) occur throughout the trial, the study will be paused to assess continuation of the study:

1. A serious adverse event (SAE) that is determined to be possibly, probably, or definitely related to the study product;
2. An adverse event (AE) related to the study product that the Principal Investigator (PI), Research Monitor (RM), and/or the sponsor's Pharmacovigilance Physician (PVG MD) agree jeopardizes the subject's health or safety;
3. An AE related to the study product that requires medical or surgical intervention to prevent occurrence of an SAE;
4. A post-infusion, abnormal coagulation function assay which is also a greater than 20% change from baseline for prothrombin time and international normalized ratio (PT/INR) and/or activated

partial thromboplastin time (aPTT) values (e.g., a subject who has a baseline INR of 1.0 with a post-infusion INR of 1.3 will activate a SR, because this is an abnormal coagulation function assay result that is also a greater than 20% change from the pre-infusion assay result); and/or

5. Post-infusion development of hemolysis or deep vein thrombosis (DVT), cardiac ischemia, or pulmonary embolism. DVT will be determined following the Institute for Clinical Systems Improvement Health Care Guideline: Venous Thromboembolism Diagnosis and Treatment (includes assessment of D-Dimer results and Wells criteria ≥ 2). (Dupras et al-2013).

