4.5.4 Conduct Exploratory Analyses Comparing FDP-ACD to FFP (Secondary Objective #2)

The analyses conducted for secondary objective #1 will be used to meet secondary objective #2. In addition, descriptive statistics on a post-infusion, abnormal coagulation function assay, which is greater than a 20% change in either direction from baseline for PT/INR and/or aPTT values, will be presented using separate shift tables. Shift tables based on the upper limit of normal (ULN) will also be provided for D-dimer, prothrombin fragment (PF) 1+2, thrombin-antithrombin complex (TAT) and C3a des Arg.

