Notes: Subjects are counted at most once on each row. Subjects may be included on more than one row.

^a=Denominator for each % is the treatment group N.

^b=Denominator adjusted because gender-specific event for males: N=XX (FDP-CPD), N=XX (FDP-ACD) for Cohort 1; N=XX (FDP-CPD), N=XX (FDP-ACD) for Cohort 2; N=XX (A), N=XX (B) for Cohort 3 [for applicable PTs].

^c=Denominator adjusted because gender-specific event for females: N=XX (FDP-CPD), N=XX (FDP-ACD) for Cohort 1; N=XX (FDP-CPD), N=XX (FDP-ACD) for Cohort 2; N=XX (A), N=XX (B) for Cohort 3 [for applicable PTs].

Preferred Terms within System Organ Class are sorted in descending order of frequency based on the treatment-emergent adverse event category.

Table 9.1. - Table 9.146. XX Measures (Units) Change from Baseline Over Time (Since Treatment Emergent Change)
XX Measures (Units) Change from Baseline Over Time (Since Treatment Emergent Change) – Cohort 1 (270 mL)
Safety Population – S3 (N=XX)

FDP-1
Phase I

	Pre-Infusion		Post-Infusion			Follow-Up Visit		
			Change from Baseline to 30 Minutes		Change from Baseline to 4 Hours		Change from Baseline to 24 Hours	
Treatment	FDP-CPD	FDP - ACD	FDP-CPD	FDP-ACD	FDP-CPD	FDP-ACD	FDP-CPD	FDP-ACD
N	xx	xx	xx	xx	xx	xx	xx	xx
Mean	xx.xx	xx.xx	xx.xx	xx.xx	xx.xx	xx.xx	xx.xx	xx.xx
SD	xx.xx	xx.xx	xx.xx	xx.xx	xx.xx	xx.xx	xx.xx	xx.xx
Min	xx.xx	xx.xx	xx.xx	xx.xx	xx.xx	xx.xx	xx.xx	xx.xx
Q1	xx.xx	xx.xx	xx.xx	xx.xx	xx.xx	xx.xx	xx.xx	xx.xx
Median	xx.xx	xx.xx	xx.xx	xx.xx	xx.xx	xx.xx	xx.xx	xx.xx
Q3	xx.xx	xx.xx	xx.xx	xx.xx	xx.xx	xx.xx	xx.xx	xx.xx
Max	xx.xx	xx.xx	xx.xx	xx.xx	xx.xx	xx.xx	xx.xx	xx.xx
>ULN ^a	xx (x.x)	xx (x.x)	xx (x.x)	xx (x.x)	xx (x.x)	xx (x.x)	xx (x.x)	xx (x.x)

Programming Note: This table has been restricted to the time points pre-infusion, 30 minutes and 4 hours post infusion at the request of the investigator, except for the hematology variables where pre-infusion, 30 minutes, 4 hours, and 24 hours will be shown. This table will be generated in the S3 population only. This table will be produced for the following endpoints where data is available:

- Vital Signs:
 - Blood Pressure (mmHg)
 - Table 9.1 (Diastolic Blood Pressure (mmHg))
 - Table 9.2 (Systolic Blood Pressure (mmHg))
 - Heart Rate (beats/min) (Table 9.3)

Note: ^a=Denominator for each % is the treatment group N at each individual time point

- Respiration Rate (breaths/min) (Table 9.4)
- Temperature (°F) (Table 9.5)
- Hematology:
 - Hematocrit (%) (Table 9.6)
 - Hemoglobin (g/dL) (Table 9.7)

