Table XX. Shift Table Summary of Number of Subjects with Absolute Laboratory Values for XX Measure (Unit) Pre-Infusion vs. Max Post-Infusion

Absolute Laboratory Values for XX Measure (Unit) Pre-Infusion vs. Max Post- Infusion – Cohort 2 (540 mL)

N=number of subjects with pre-infusion ‘normal’ and at least one post-infusion value; n=among the ‘N’, number of subjects with Max. post-infusion ‘high’. High will be a greater than or equal to 20% increase from pre-infusion for PT, INR and aPTT and greater than the upper limit of normal (ULN) for all other endpoints except for D-Dimer. Normal will be a less than 20% increase from pre-infusion for PT, INR, and aPTT and lower than or equal to the ULN for all other endpoints except for D-Dimer. D-Dimer will be converted to a categorical variable where normal will be < 0.5 ug/mL FEU and high will be \geq 0.5 ug/mL FEU.

80

Program Path:

Data source:AD LB Cross Reference: Listing 26-27

Data extract date:

Safety Population – S3 (N=XX)

FDP-1

Phase I

Programming Note: For Cohort 3, the treatment arms will be unmasked for final data analysis once the study has been unblinded. This table will be produced for the following endpoints for Cohort 3 for the first infusion (Table 11.9-11.15):

- Coagulation Factor Tests:
 - PT (Table 11.9)
 - INR (Table 11.10)
 - aPTT (Table 11.11)
 - D-Dimer (ug/mL FEU) (Table 11.12)
 - PF 1+2 (pmol/L) (Table 11.13)
 - TAT (ng/mL) (Table 11.14)
 - C3a des Arg (ng/mL) (Table 11.15)

Programming Note: This table will be produced for the following endpoints for Cohort 3 for the second infusion (Table 11.16-11.22):

- Coagulation Factor Tests:
 - PT (Table 11.16)
 - INR (Table 11.17)
 - aPTT (Table 11.18)
 - D-Dimer (ug/mL FEU) (Table 11.19)
 - PF 1+2 (pmol/L) (Table 11.20)
 - TAT (ng/mL) (Table 11.21)
 - C3a des Arg (ng/mL) (Table 11.22)

Programming Note: For Cohort 3, the treatment arms will be unmasked for final data analysis after the study has been unblinded.

Table XX. Shift Table Summary of Number of Subjects with Absolute Laboratory Values for XX Measure (Unit) Pre-Infusion vs. Max Post-Infusion

Absolute Laboratory Values for XX Measure (Unit) Pre-Infusion vs. Max Post- Infusion – Cohort 3 (810 mL) – Infusion #1 Safety Population – S3 (N=XX)

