N=number of subjects with pre-infusion ‘normal’ and at least one post-infusion value; n=among the ‘N’, number of subjects with Max. post-infusion ‘high’. High will be a greater than or equal to 20% increase from pre-infusion for PT, INR and aPTT and greater than the upper limit of normal (ULN) for all other endpoints except for D-Dimer. Normal will be a less than 20% increase from pre-infusion for PT, INR, and aPTT and lower than or equal to the ULN for all other endpoints except for D-Dimer. D-Dimer will be converted to a categorical variable where normal will be < 0.5 ug/mL FEU and high will be \geq 0.5 ug/mL FEU.

81

Program Path:

Data source:AD LB Cross Reference: Listing 26-27

Data extract date:

FDP-1
Phase I

**Table XX. Shift Table Summary of Absolute Laboratory Values for XX Measure (Unit) Pre-Infusion vs. Max Post-Infusion
Absolute Laboratory Values for XX Measure (Unit) Pre-Infusion vs. Max Post- Infusion – Cohort 3 (810 mL) – Infusion #2
Safety Population – S3 (N=XX)**

FDP-1
Phase I

N=number of subjects with pre-infusion ‘normal’ and at least one post-infusion value; n=among the ‘N’, number of subjects with Max. post-infusion ‘high’. High will be a greater than or equal to 20% increase from pre-infusion for PT, INR and aPTT and greater than the upper limit of normal (ULN) for all other endpoints except for D-Dimer. Normal will be a less than 20% increase from pre-infusion for PT, INR, and aPTT and lower than or equal to the ULN for all other endpoints except for D-Dimer. D-Dimer will be converted to a categorical variable where normal will be < 0.5 ug/mL FEU and high will be \geq 0.5 ug/mL FEU.

82

Programming Note: These tables will also be repeated for Treatment Emergent Low for PT, INR, and aPTT only. Low will be defined as a greater than or equal 20% decrease from pre-infusion. N=Number of subjects with pre-infusion 'normal' and at least one post-infusion value; n=among the 'N,' number of subjects with Min. post-infusion 'low.' Normal will be a less than 20% decrease from pre-infusion for PT, INR and aPTT (Table 11.23 – Table 11.34). The titles are listed below:

Table XX. Shift Table Summary of Number of Subjects with Absolute Laboratory Values for XX Measure (Unit) Pre-Infusion vs. Min Post-Infusion

Absolute Laboratory Values for XX Measure (Unit) Pre-Infusion vs. Min Post-Infusion – Cohort 1 (540 mL)

Safety Population – S3 (N=XX)

FDP-1

Phase I

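### The PT, INR and aPTT shift-table footnotes count every change of 20% or more, a wider event than the abnormal result with a change above 20% that the SAP and protocol text promise

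*SAP*

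**What the plan says.** The text of both documents describes the event in almost the same words. SAP 4.5.4 (the second section with that number, on secondary objective #2) announces "descriptive statistics on a post-infusion, abnormal coagulation function assay, which is greater than a 20% change in either direction from baseline" for PT/INR and/or aPTT, to be shown in separate shift tables. Protocol 11.1.2.2 announces "descriptive statistics on a post-infusion, abnormal coagulation function assay that is greater than a 20% change in either direction from baseline".

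The Table 11 footnotes in SAP section 5 define the counts. For increases: "High will be a greater than or equal to 20% increase from pre-infusion for PT, INR and aPTT". The upper limit of normal (ULN) is applied only to the remaining endpoints, and D-dimer has its own cut-off. For decreases: "Low will be defined as a greater than or equal 20% decrease from pre-infusion". The denominator N is limited to subjects whose pre-infusion value is normal, and for these tests "Normal will be a less than 20% increase from pre-infusion for PT, INR, and aPTT"; the Low tables use the mirror image. The footnotes are the same for all three cohorts.

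Stopping rule 4 uses a closely related phrase. The protocol synopsis has "A post-infusion, coagulation function assay result that is abnormal and also greater than a 20% change from the baseline value", and SAP 1.1 has "abnormal coagulation function assay which is also a greater than 20% change from baseline".

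**The concern.** Apart from the ULN-based tables for other markers, these shift tables are the only output added for secondary objective 2 beyond the objective 1 analyses. A reader who takes the event from the SAP text and the counts from Table 11 would believe that each counted subject had an abnormal coagulation result. The footnotes do not require that. They also admit a change of exactly 20%, which the text leaves out, and their baseline condition cannot be applied in any meaningful way.

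No other planned summary table supplies the joint event. Table 9 has a row for values above the ULN, and it is produced for PT, INR and aPTT at both Cohort 3 infusions. However, its programming note says "This table has been restricted to the time points pre-infusion, 30 minutes and 4 hours post infusion at the request of the investigator", with an exception for hematology only, while SAP Table 5 schedules these three tests for analysis at 24 hours and 28 days as well. Table 9 has no row for values below the lower limit of normal (LLN), and it does not link the ULN to the 20% change. Figures 4.1 to 4.3 plot individual values but give no counts.

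**Working it through.** **Inputs.** Baseline is the value taken just before infusion at the Infusion Visit (SAP 4.4.2). The two definitions are those quoted above. The documents give no laboratory limits and no INR precision, so I assume INR to one decimal and two reference ranges, 0.9–1.1 and 0.8–1.2.

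**Formula.** Percent change = (post − pre) / pre × 100.

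**The plan's own example.** INR 1.0 to 1.3: (1.3 − 1.0) / 1.0 = +30%. This is above 20%, as the documents say, and counts under both definitions if 1.3 is above the ULN, as the example implies.

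**Results on which the definitions differ.**
- INR 1.0 to 1.2: 0.2 / 1.0 = +20.0%. High by the footnote; not an event by the text, since it does not exceed 20%.
- INR 0.9 to 1.1: 0.2 / 0.9 = +22.2%. High by the footnote; within both assumed ranges, so not an event by the text.
- INR 1.0 to 0.8: −0.2 / 1.0 = −20.0%. Low by the footnote; not an event by the text.

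**The baseline condition.** A pre-infusion value compared with itself changes by (pre − pre) / pre = 0%, always below 20%. Every subject with a pre-infusion value is therefore normal, and the condition excludes nobody.

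**Which pairs differ.** Take all 9 × 9 = 81 baseline/post pairs of INR from 0.7 to 1.5, in exact fractions. The stated event is High if above the ULN and more than +20%, and Low if below the LLN and more than −20%.

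| Assumed range | Baselines | High: footnote vs stated | Low: footnote vs stated | Stated events missed by footnote |
|---|---|---|---|---|
| 0.9–1.1 | all | 25 vs 18 | 23 vs 12 | 0 |
| 0.9–1.1 | in range only | 11 vs 9 | 5 vs 4 | 0 |
| 0.8–1.2 | all | 25 vs 15 | 23 vs 7 | 0 |
| 0.8–1.2 | in range only | 18 vs 12 | 8 vs 4 | 0 |

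The rows for in-range baselines are the more relevant ones for healthy volunteers. The pairs are unweighted: they show where the definitions part, not how often subjects will fall there. That none is missed does not depend on the grid, because any result beyond a limit and changed by more than 20% has also changed by at least 20%.

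**Weight of one subject.** With 4 subjects planned per sequence, 1 / 4 = 25 percentage points.

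**Tables concerned.** 3 tests × 2 infusions × 2 directions = 12 Cohort 3 tables.

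**Boundary arithmetic.** In ordinary floating point (1.2 − 1.0) / 1.0 evaluates to 0.19999999999999996, so a program testing for at least 0.20 would not flag an exact 20% rise. The boundary needs a rounding rule whichever inequality is chosen.

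**The case against.** The best objection is that *abnormal* in the text means no more than the 20% change. The sentence that follows in both Protocol 11.1.2.2 and SAP 4.5.4 announces ULN-based shift tables for D-dimer, PF 1+2, TAT and C3a des Arg. That suggests a deliberate split between range-based tables for those markers and change-based tables for PT, INR and aPTT, and Table 11 follows such a split. This reading is possible. Against it, stopping rule 4 uses nearly the same phrase and joins the two conditions with *also*, and Listings 28 and 29 define their abnormal flag by the laboratory limits. On either reading the conflict between more than 20% and at least 20% remains, and so does the circular definition of normal.

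A second objection is that the consequence is small. The sections are headed exploratory, no hypothesis is tested, and with eight Cohort 3 subjects the joint event can be rebuilt from Listings 28 and 29. That is true, and it limits the weight of the point without removing the mismatch.

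A reader might infer from the circular baseline condition that Table 11 would lose many qualifying events. The documents do not support that. Large losses arise only if a programmer overrules the footnote and requires a baseline within a two-sided reference range: on the full grid with range 0.9–1.1, 9 of 18 High and 8 of 12 Low events would then drop out. The footnote explicitly reserves the ULN for other endpoints, and the only range-based normal it contains is one-sided. Applying that form (baseline at or below the ULN, mirrored to at or above the LLN for Low) loses 1 of 18 and 0 of 12, and none with range 0.8–1.2. Followed as written, the footnote loses none.

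**Conclusion.** The point holds as a mismatch between text and table definitions. The Table 11 footnotes for PT, INR and aPTT do not implement the event in SAP 4.5.4 and Protocol 11.1.2.2. Read literally, they count a superset of it: results changed by exactly 20%, and results changed by 20% or more that stay within the reference range, are added, and no stated event is lost. The circular normal is a wording defect with no numerical effect if followed literally.

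The frequency of extra counts cannot be derived from the documents; the examples and grid rest on assumed INR limits and one-decimal reporting, and they cover INR only. With 4 subjects per sequence, a single extra count is visible as 25 percentage points.

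The footnotes run across all three cohorts, but the stated event belongs to the Cohort 3 comparison of FDP-ACD with FFP. It would be wrong to infer any effect on safety decisions: the stopping rule is stated separately, and SAP 4.5.3 limits the DSMB tables to 1.1 through 8.3, which leaves Table 11 out. The correction should be made before final programming.

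**What to change.** For Tables 11.9–11.11 and 11.16–11.18, and the six Cohort 3 Low tables within 11.23–11.34:

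- **High:** maximum post-infusion value above the ULN and more than 20% above that infusion's pre-infusion value.
- **Low:** minimum post-infusion value below the LLN and more than 20% below it.
- **N:** subjects with a pre-infusion value and at least one post-infusion value, in place of the circular normal, showing how many had an out-of-range baseline.
- **Boundary:** state the rounding rule used for the 20% comparison.
- **Optional:** keep the change-only count as a separately labelled line.

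If the sponsor meant a change-only event, delete *abnormal* from Protocol 11.1.2.2 and SAP 4.5.4, use one inequality in text and footnotes, and still replace the circular normal.

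The cost is footnote text and one programming condition per direction. The Max and Min titles can stay, and the ranges and H/L flags are already in Listings 28 and 29. Compared with the literal footnote, N does not change, and counts stay the same or fall. In the same edit, the Table 11 cross-reference to Listings 26–27, which are urinalysis, should point to Listings 28–29.

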#### 6.4.2. Secondary Endpoints

The following secondary endpoints will only be evaluated in Cohort 3 subjects:

• Change in pre- and post-infusion values for Prothrombin Time and International Normalized Ratio (PT/INR), aPTT, Factors I, II, V, VII, VIII, IX, X, XI, D-DIMER, von Willebrand Factor activity, Protein S activity, Protein C activity, Prothrombin

Fragments 1+2 (PF 1+2), Thrombin/Antithrombin (TAT), Antithrombin III (AT-III), Alpha-2 antiplasmin, and C3a des Arg activity compared to pre-infusion values after infusion of 3 units of FDP compared to 3 units of FFP; and

• Determine if the changes in specific hematology, urinalysis, vital signs, DAT, and chemistry values are similar within clinically meaningful levels after infusion of either 3 units of autologous FDP or FFP.

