4.5.4 Conduct Safety Analyses Comparing FDP-ACD to FFP (Secondary Objective #1)

Using Cohort 3 data, descriptive statistics similar to those described in Section 4.5.3 will be presented for the change between baseline and each time point, where appropriate, of the safety endpoint measures shown in Table 5. Descriptive statistics will be provided for each type of plasma product treatment, treatment period, and treatment sequence arm (FDP-ACD then FFP [Sequence 1] or FFP then FDP-ACD [Sequence 2]). The mean and standard deviation at each time point for each treatment group, based on the original values, will be exhibited in figures. Color-coded spaghetti plots will display by treatment group individual data for each subject over time.

Definitions for Secondary Objectives

- Change from baseline: (Post-baseline value – baseline value).
- Body mass index (kg/m^2): $\text{weight} (\text{kg})/(\text{height} (\text{cm})/100)^2$.
- Total amount administered per kg of weight (ml/kg): total amount administered (ml)/weight (kg).

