The title for Cohort 3 for the second infusion is shown below:

Table XX.XX Measures (Units) Change from Baseline Over Time Since Treatment Emergent Change
XX Measures (Units) Change from Baseline Over Time Since Treatment Emergent Change – Cohort 3 (810 mL) – Infusion #2
Safety Population – S3 (N=XX)
FDP-1
Phase I

Note: ^a=Denominator for each % is the treatment group N at each individual time point

76

Program Path:

Data source: ADVS, ADLB Cross Reference: Listing 10-12, Listing 20-23, Listing 26-27

Data extract date:

Table 10.1. – Table 10.36. XX Measures (Percentage) Over Time Since Treatment Emergent Change
XX Measures (Percentage) Over Time Since Treatment Emergent Change – Cohort 1 (270 mL)

Safety Population – S3 (N=XX)

FDP-1

Phase I

Treatment	Pre-Infusion		Post-Infusion			
			30 min		4 hrs	
	FDP-CPD	FDP-ACD	FDP-CPD	FDP-ACD	FDP-CPD	FDP-ACD
n ^a	xx	xx	xx	xx	xx	xx
Negative	xx (x.x)	xx (x.x)	xx (x.x)	xx (x.x)	xx (x.x)	xx (x.x)
Positive	xx (x.x)	xx (x.x)	xx (x.x)	xx (x.x)	xx (x.x)	xx (x.x)

^aNumber of subjects with non-missing data, used as the denominator

Programming Note: This table has been restricted to the time points pre-infusion, 30 minutes and 4 hours post infusion at the request of the investigator. This table will be produced for the following endpoints where data are available:

- Urinalysis:
 - Glucose (Table 10.1)
 - Ketones (Table 10.2)
 - Protein (Table 10.3)
 - Blood (Table 10.4)
 - Leukocyte esterase (Table 10.5)
 - Nitrite (Table 10.6)
 - Bilirubin (Table 10.7)
- Direct Antiglobulin Test (DAT):
 - Immunoglobulin G (Table 10.8)
 - Complement C3 (Table 10.9)

Programming Note: This table will be repeated for Cohort 2 (Table 10.10-10.18) as follows:

- Urinalysis:

Note: a=Denominator for each % is the treatment group N.

Program Path:

Data source:ADLB Cross Reference: Listing 24-25, Listing 28

Data extract date:

- Glucose (Table 10.10)
- Ketones (Table 10.11)
- Protein (Table 10.12)
- Blood (Table 10.13)
- Leukocyte esterase (Table 10.14)
- Nitrite (Table 10.15)
- Bilirubin (Table 10.16)
- Direct Antiglobulin Test (DAT):
 - Immunoglobulin G (Table 10.17)
 - Complement C3 (Table 10.18)

The title for Cohort 2 are listed below:

Table XX. Measures (Percentage) Over Time Since Treatment Emergent Change
XX Measures (Percentage) Over Time Since Treatment Emergent Change – Cohort 2 (540 mL)
Safety Population – S3 (N=XX)
FDP-1
Phase I

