	Missing	XX	XX	XX	XX	XX	XX	XX
Total Amount Administered per kg of weight (mL/kg) – Infusion #1								
	n ^a	XX	XX	XX	XX	XX	XX	XX
	Mean	XX.X	XX.X	XX.X	XX.X	XX.X	XX.X	XX.X
	SD	XX.X	XX.X	XX.X	XX.X	XX.X	XX.X	XX.X
	Median	XX.X	XX.X	XX.X	XX.X	XX.X	XX.X	XX.X
	Q1, Q3	XX,XX	XX,XX	XX,XX	XX,XX	XX,XX	XX,XX	XX,XX
	Min, Max	XX,XX	XX,XX	XX,XX	XX,XX	XX,XX	XX,XX	XX,XX
	Missing	XX	XX	XX	XX	XX	XX	XX
Total Amount Administered (mL) – Infusion #2 (Cohort 3 only)								
	n ^a					XX	XX	XX

Note: Abbreviations: N=number of subjects in the population; Q1=25% Percentile; Q3=75% Percentile; SD=Standard Deviation.

^a=Number of subjects with non-missing data, used as the denominator.

[figure not shown]
		FDP- CPD (270 mL) N=XX	FDP- ACD (270 mL) N=XX	FDP- CPD (540 mL) N=XX	FDP- ACD (540 mL) N=XX	FDP-ACD X FFP (810 mL) N=XX	FFP X FDP-ACD (810 mL) N=XX	Overall N=XX
	Mean					xx.x	xx.x	xx.x
	SD					xx.x	xx.x	xx.x
	Median					xx.x	xx.x	xx.x
	Q1, Q3					xx,xx	xx,xx	xx,xx
	Min, Max					xx,xx	xx,xx	xx,xx
	Missing					xx	xx	xx
Total Amount Administered per kg of weight (mL/kg) – Infusion #2 (Cohort 3 only)								
	n ^a					xx	xx	xx
	Mean					xx.x	xx.x	xx.x
	SD					xx.x	xx.x	xx.x
	Median					xx.x	xx.x	xx.x
	Q1, Q3					xx,xx	xx,xx	xx,xx
	Min, Max					xx,xx	xx,xx	xx,xx
	Missing					xx	xx	xx

Programming Note: Grayed out cells mean no data is expected. For Cohort 3, the treatment arms will be unmasked for final data analysis once the study has been unblinded.

Note: Abbreviations: N=number of subjects in the population; Q1=25% Percentile; Q3=75% Percentile; SD=Standard Deviation.

^a=Number of subjects with non-missing data, used as the denominator.

Figure 3.1.-3.5. XXX Measure (Units): Cohort 3 FDP-ACD vs. FFP: Means and Standard Deviations Over Time
Safety Population – S3 (N=XX)
FDP-1
Phase I

[figure not shown]
Programming Note: This figure will be repeated for the following vital sign endpoints:

- Temperature (°F) (Figure 3.1)
- Heart Rate (beats/min) (Figure 3.2)
- Diastolic Blood Pressure (mmHg) (Figure 3.3)
- Systolic Blood Pressure (mmHg) (Figure 3.4)
- Respiratory Rate (breaths/min) (Figure 3.5)

For Cohort 3, the treatment arms will be unmasked for final data analysis once the study has been unblinded.

Note: This figure displays the mean +/- the standard deviation at each time point.

Figure 4.1-4.19. XXX Measures (Units): Cohort 3 FDP-ACD x FFP Spaghetti Plots
Safety Population – S3 (N=XX)
FDP-1
Phase I

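### SAP Tables 10.1–10.36 give only marginal positive counts, so no planned summary table shows within-subject change for the seven qualitative urinalysis tests

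*SAP*

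**What the plan says.** Protocol 6.4.2 sets this aim for Cohort 3: "Determine if the changes in specific hematology, urinalysis, vital signs, DAT, and chemistry values are similar within clinically meaningful levels", comparing three units of FDP with three units of FFP. SAP Section 4.5.4 (Secondary Objective #1) says descriptive statistics "will be presented for the change between baseline and each time point, where appropriate, of the safety endpoint measures shown in Table 5". SAP Table 5 lists urine glucose, ketones, protein, blood, leukocyte esterase, nitrite and bilirubin at pre-infusion, 0.5 hours and 4 hours. SAP 4.4.2 takes the value just before infusion as baseline.

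The summary table for these tests is Table 10, titled "XX Measures (Percentage) Over Time Since Treatment Emergent Change". Its shell has three rows (n, Negative, Positive) under each treatment at three times. The programming note explains the times: "This table has been restricted to the time points pre-infusion, 30 minutes and 4 hours post infusion at the request of the investigator". One note gives the denominator as "Number of subjects with non-missing data, used as the denominator"; another note under the same shell gives it as the treatment group N.

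Table 11 is built differently. Its N is the "number of subjects with pre-infusion ‘normal’ and at least one post-infusion value", and its n is the number of those whose maximum post-infusion value is high. It is used only for coagulation and related markers. The text for Secondary Objective #2 names PT/INR and aPTT, and adds that "Shift tables based on the upper limit of normal (ULN) will also be provided for D-dimer", PF 1+2, TAT and C3a des Arg.

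**The concern.** Table 10's title speaks of treatment-emergent change, but the shell contains no change. It compares the number of subjects positive before infusion with the number positive after, and these may be different subjects. If one subject turns positive while another's baseline positive clears, the two percentages are equal and the row looks unchanged.

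What is at stake is the urinalysis part of the secondary comparison. With four subjects per arm, one conversion is the whole finding, and the planned summary may be unable to say whether there was one. The SAP already has a layout that answers the question and does not apply it to these tests.

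**Working it through.** **1. Does any other summary output fill the gap?** From the table lists and programming notes in SAP Section 5:

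| Output | Covers | Within-subject urinalysis change? |
|---|---|---|
| Table 9 | vital signs, hematology, chemistry, coagulation | no urinalysis |
| Table 10 | 7 urinalysis tests and 2 DAT results | marginal counts only |
| Table 11 | PT, INR, aPTT, D-dimer; in Cohort 3 also PF 1+2, TAT, C3a des Arg | no urinalysis |
| Table 12 | hematology, chemistry, coagulation (Cohort 3) | no urinalysis |
| Table 13 | DAT, pre-infusion only | no urinalysis |
| Figures 3 and 4 | vital signs; coagulation | no urinalysis |

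The inventory matches the table numbering. Table 10 has (7 + 2) tests × 4 sets (Cohort 1, Cohort 2, and Cohort 3 at each infusion) = 36. Table 11 has 4 + 4 + 7 + 7 for high values plus 3 × 4 = 12 for low values, which is 34.

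**2. What can be recovered from Table 10?** Let a column hold n subjects with complete data, B positive before infusion and P positive at one later time. The number of new positives is only bounded:

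max(0, P − B) ≤ new positives ≤ min(P, n − B).

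Columns hold n = 4. SAP Table 1 has four subjects per arm, and Cohort 3 is tabulated separately for Infusion #1 and Infusion #2.

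- B = 0: both bounds equal P, so every new positive shows.
- B = 1, P = 1: lower bound max(0, 0) = 0, upper bound min(1, 3) = 1. The table reads 25% both times; the truth is 0 of 3 or 1 of 3 (0% or 33%).
- B = 2, P = 2: lower bound 0, upper bound min(2, 2) = 2. The truth is anywhere from 0 of 2 to 2 of 2.

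This step needs no assumption about rates.

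**3. How often might it happen?** The documents give no baseline positivity, clearance or conversion rates. The following is an illustration, by exact enumeration for n = 4 at one time point. It assumes that 10% of negatives convert and that either 50% or 20% of baseline positives clear. A conversion is masked when at least as many subjects clear as convert.

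| Assumed baseline positivity | P(at least one new positive) | P(a conversion occurs and is masked), 50% clear | P(masked, given a conversion), 50% clear | Same, 20% clear |
|---|---|---|---|---|
| 0% | 34.4% | 0% | 0% | 0% |
| 5% | 32.9% | 2.3% | 6.9% | 2.8% |
| 10% | 31.4% | 4.2% | 13.5% | 5.6% |
| 25% | 26.8% | 8.4% | 31.5% | 13.6% |
| 40% | 21.9% | 10.3% | 47.0% | 21.4% |

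For example, at 10% positivity P(at least one new) = 1 − (1 − 0.9 × 0.1)⁴ = 0.314, and 0.0424 / 0.314 = 13.5%. With 25% of negatives converting and 50% clearing, the conditional figures at 10%, 25% and 40% positivity are 12.0%, 28.7% and 43.7%. Masking across the whole row would also need the offset to hold at both 30 minutes and 4 hours if the new positive is present at both.

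**4. DAT rows.** Protocol Tables 7 and 9 schedule DAT at pre-infusion, 24 hours and Day 28. Table 10 shows 30 minutes and 4 hours. For Cohort 3, protocol 8.2.2 lists DAT among the tests done at 30 minutes and 4 hours, which disagrees with protocol Table 9. Protocol Table 15 marks DAT at pre-infusion and 24 hours; SAP Table 5 marks pre-infusion only.

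**The case against.** The strongest reply is that nothing is lost. Listings 25 and 27 print every qualitative urinalysis result by subject and visit, and with four subjects per arm a conversion can be read by eye. A finding recorded as an adverse event that was absent before treatment counts as a TEAE under SAP 4.5.3 and enters Listing 13 and the TEAE tables. This stands, and it rules out the stronger reading a reader might draw, that a new positive could never appear as treatment-emergent. But the listings carry no comparison with baseline, and the adverse event route depends on the finding being reported as an event. Neither is a change summary.

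A reader might also infer that the stopping rule for hemolysis, or dose escalation, rests on this table. The documents do not support that. The rule is triggered by an event in a subject, and protocol 10.5.1 has hemolysis documented from laboratory results. Under SAP 4.5.3 the DSMB package is Tables 1.1–8.3 (without 7.4–7.6) and Figures 1 and 2, so Table 10 is not in it. Red urine appears in protocol 5.6.1.4 among other rare side effects, not among the expected risks of FDP infusion.

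Next, the change commitment is qualified to cases where it is appropriate, and SAP 4.5.1 specifies frequencies and percentages for categorical measures, which Table 10 supplies. The protocol's change endpoint covers Cohort 3 only. So this is not a plain breach. Still, no reason is given why change would be inappropriate for a negative/positive result, and the table's own title claims it.

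Finally, the rates in step 3 are assumed. Known kidney disease is excluded and urinalysis is done at screening, so baseline positivity may be low and masking rare.

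**Conclusion.** The point holds as a gap in the planned summaries. For the seven urinalysis tests, no summary table gives within-subject change, and Table 10 cannot be made to yield it unless the baseline count is zero or the margins happen to fix the answer. That conclusion rests on the shells and on arithmetic alone. In a four-subject column the ambiguity is 0 of 3 against 1 of 3 when one subject is positive both before and after, and 0 of 2 up to 2 of 2 when two are.

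The frequency is unknown. Under the assumed rates with 10% of negatives converting, a column hides a conversion in about 4% to 10% of cases at 10% to 40% baseline positivity and 50% clearance, less if clearance or positivity is lower, and never at zero positivity. The issue concerns end-of-study reporting. It does not affect subject-level safety monitoring, the pausing rules or the DSMB reviews.

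**What to change.** For each of the seven urinalysis tests in Tables 10.1–10.36, add a row with n/N newly positive. N is the number of subjects negative before that infusion with a post-infusion result, and n is the number of those who become positive. Give it at 30 minutes, at 4 hours and at any post-infusion time point, stating whether the last includes the 24-hour sample. Show it by product infused, and keep the marginal percentages. Borrow only the at-risk layout from Table 11: its definition of normal for PT, INR and aPTT is itself a change from pre-infusion and should not be carried over.

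Choose one of the two Table 10 denominator notes and delete the other. For DAT, give the newly positive count only at post-infusion times where the schedule collects it, after reconciling protocol 8.2.2 with protocol Table 9 on Cohort 3 timing, and align SAP Table 5 and protocol Table 15 with the outcome.

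The cost is shell wording and a few lines of programming for the urinalysis rows, plus a clarification of the DAT schedule. The urinalysis count uses data already collected.
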